Annual reviews. The Principal Investigator ([name], MD) will review this protocol on a continuing basis for subject safety and provide written summary of results annually for review in the annual progress reports submitted to the IRB's, and safety officer, FDA and American Diabetes Association (Sponsor).

Annual reports. The annual report will include a list of adverse events. These will be provided to the institutional review boards. Annual reports will be generated both site specific and for the overall conduct of the trial. *Content of annual reports:* The annual report will address: (1) whether adverse event rates are consistent with pre-study assumptions; (2) reason for dropouts from the study; (3) whether all participants met entry criteria; (4) whether continuation of the study is justified on the basis that additional data are needed to accomplish the stated aims of the study; and (5) conditions whereby the study might be terminated prematurely.

Laboratory review: Laboratory assessment will be performed at scheduled and predetermined intervals. The study investigators will review all laboratory reports within 24 hours of completion by the laboratory for participant safety.

Rules for stopping the trial in the event that expected or unexpected adverse events arise, particularly, but not exclusively, as explained in the Risks and Discomforts section of Protocol and its Informed Consent.

Study therapy should be discontinued for any of the following reasons:

- a. Subject decision to withdraw consent for study participation
- b. New diagnosis of exclusionary medical condition
- c. Evidence of allergy to administered products
- d. Acute change in renal function (eGFR decline >50%, validated) or liver function (> 3-fold increase in ALT or AST)
- e. Intolerable adverse event as judged by investigator and participant
- f. Pregnancy or unwillingness to use appropriate contraception.

The trial may be stopped by the regulatory oversight committees including, but not limited to the IRB, American Diabetes Association, or FDA.

Describe the plan to be followed by the Principal Investigator/study staff for review of adverse events experienced by subjects under his/her care, and when applicable, for review of sponsor safety reports and DSMB reports. Describe the plan for reporting adverse events to the sponsor and the Partners' IRB and, when applicable, for submitting sponsor safety reports and DSMB reports to the Partners' IRBs. When the investigator is also the sponsor of the IND/IDE, include the plan for reporting of adverse events to the FDA and, when applicable, to investigators at other sites.

NOTE: In addition to the adverse event reporting requirements of the sponsor, the principal investigator must follow the Partners Human Research Committee guidelines for Adverse Event Reporting

See above

MONITORING AND QUALITY ASSURANCE

Describe the plan to be followed by the principal investigator/study staff to monitor and assure the validity and integrity of the data and adherence to the IRB-approved protocol. Specify who will be responsible for monitoring, and the planned frequency of monitoring. For example, specify who will review the accuracy and completeness of case report form entries, source documents, and informed consent.

NOTE: Regardless of monitoring plans by the sponsor or others, the principal investigator is ultimately responsible for ensuring that the study is conducted at his/her investigative site in accordance with the IRB-approved protocol, and applicable regulations and requirements of the IRB.

See above

For guidance, refer to the following Partners policies:

Data and Safety Monitoring Plans and Quality Assurance
<http://healthcare.partners.org/phsirb/guidance.htm#13>

Reporting Unanticipated Problems (including Adverse Events)
<http://healthcare.partners.org/phsirb/guidance.htm#7>

PRIVACY AND CONFIDENTIALITY

Describe methods used to protect the privacy of subjects and maintain confidentiality of data collected. This typically includes such practices as substituting codes for names and/or medical record numbers; removing face sheets or other identifiers from completed surveys/questionnaires; proper disposal of printed computer data; limited access to study data; use of password-protected computer databases; training for research staff on the importance of confidentiality of data, and storing research records in a secure location.

NOTE: Additional measures, such as obtaining a Certificate of Confidentiality, should be considered and are strongly encouraged when the research involves the collection of sensitive data, such as sexual, criminal or illegal behaviors.

Research data will be obtained in the form of medical history and review of selected medical record information including personal and family history including personal and family history, anthropometric measurements, laboratory tests, questionnaires. Data will be collected by study staff and stored in computerized databases. Only those involved directly with the study and patient care will have access to any data collected. Computer files with subject information will be kept locked with restricted access. No information about a subject will be shared with other parties unless the subject has given written or witnessed consent to do so.

SENDING SPECIMENS/DATA TO RESEARCH COLLABORATORS OUTSIDE PARTNERS

Specimens or data collected by Partners investigators will be sent to research collaborators outside Partners, indicate to whom specimens/data will be sent, what information will be sent, and whether the specimens/data will contain identifiers that could be used by the outside collaborators to link the specimens/data to individual subjects.

Specimens collected for this protocol will be procured and processed at laboratories including those at BWH, the Joslin and Quest Diagnostic, the Catalyst Core laboratory and LabCorp. Health data will be shared by the investigative teams at the Joslin Diabetes Center and Brigham and Women's Hospital. All investigators and study staff will be trained in the ethical conduct of clinical research and privacy protection practices and credentialed by their institutions for the level of their staff positions. Biospecimens obtained at the time of the study visits will be stored at the Joslin Diabetes Center for batch analysis. Data may be analyzed at a later date for cost effectiveness as described in the protocol. Clinical research specimens and research level data will be labeled with a unique identifier. However, as clinical care is coordinated at two institutions and in a certified clinical laboratory (Quest and/or LabCorp. A study nickname and numeric code will be used, but Date of Birth must be provided for age relevant normative interpretation. It is hard to identify an individual in the New England Area based solely on DOB.

Some specimens will be saved for batch analysis in core laboratories. Samples will be stored at the Joslin Diabetes Center. The Joslin Diabetes Center has ceded review to Partners. Application ID: 1291 - Metabolic Effects of Betaine Supplementation, August 16th, 2013.

Specifically address whether specimens/data will be stored at collaborating sites outside Partners for future use not described in the protocol. Include whether subjects can withdraw their specimens/data, and how they would do so. When appropriate, submit documentation of IRB approval from the recipient institution.

RECEIVING SPECIMENS/DATA FROM RESEARCH COLLABORATORS OUTSIDE PARTNERS

When specimens or data collected by research collaborators outside Partners will be sent to Partners investigators, indicate from where the specimens/data will be obtained and whether the specimens/data will contain identifiers that could be used by Partners investigators to link the specimens/data to individual subjects. When appropriate, submit documentation of IRB approval and a copy of the IRB-approved consent form from the institution where the specimens/data were collected.

Specimens obtained during the study of “Metabolic Effects of Betaine Supplementation” will be labeled with unique alpha numeric identifier. Samples may be assayed in clinical or core laboratories at Partner’s Healthcare, Joslin, or Quest or LabCorp laboratories. Only CLIA certified labs will be used for safety measures.

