Phlebotomy blood loss and discomfort with required laboratory blood draws and intravenous catheters. Bleeding, bruising or phlebitis at the site of venipuncture are also a possibilities. *Blood loss:* The total amount of blood drawn during the protocol is approximately 650 ml. This is approximately equal to 1 1/2 units of blood. One unit is the volume typically donated at a single visit to a blood bank, and can be donated every other month. In this study phlebotomy will be distributed over each visit spanning three months. Thus, phlebotomy does not exceed the rate of 1 unit per month and should not present a significant stress to any individual. Volunteers will be requested not to donate blood within 2 months after the study. Any subject who has just donated blood will be asked to postpone entry to the study until 2 months have elapsed.

Screening tests and procedures It is possible that as a result of the screening process a subject may learn that they have a health disorder that they were unaware they had. Every effort will be made to help the participant obtain the care that they need.

Breach of Confidentiality While every effort will be made to protect the confidentiality of participant identifiable information, there is the potential loss of confidentiality by participating in this study.

Inconvenience and Unknown Risks Participants may be inconvenienced by the time commitment involved in participation in the study. There may be other risks from this study not yet identified.

Participants can choose not to participate in the clinical research project and can withdraw consent at any time.

Describe explicitly the methods for ensuring the safety of subjects. Provide objective criteria for removing a subject from the study, for example, objective criteria for worsening disease/lack of improvement and/or unacceptable adverse events. The inclusion of objective drop criteria is especially important in studies designed with placebo control groups.

Participants will be withdrawn from the study for the following reasons:

- a. Subject decision to withdraw consent for study participation
- b. Evidence of allergy to administered products
- c. Acute change in renal function (eGFR decline >50%, validated) or liver function (> 3-fold increase in ALT or AST)
- d. New diagnosis of exclusionary medical condition
- e. Intolerable adverse event as judged by investigator and participant

FORESEEABLE RISKS AND DISCOMFORTS

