NOTE: Regardless of data and safety monitoring plans by the sponsor or others, the principal investigator is ultimately responsible for protecting the rights, safety, and welfare of subjects under his/her care.

In brief, the Principal Investigator, [name], will be responsible for ensuring that the study is conducted in accordance with the IRB approved protocol and will review all adverse events, serious adverse events. The study nurse coordinator will also perform a periodic review on all data. The members of the study team will conduct regularly scheduled meeting approximately weekly as well as on an add needed basis to review status of the trial inclusive of enrollment, oversight of informed consent, general conduct of the trial as well as reporting of any complications as needed to the NIH or IRB as stated below.

All adverse events will be reported to the IRB.

- Serious adverse events including death, life-threatening experience, event resulting in hospitalization, event resulting in an intervention, and event resulting in congenital anomaly/birth defect will be reported within 24 hours followed by a full written report within one week by the principal investigator.
- Adverse events and unanticipated problems will be reported per PHRC reporting guidelines.
- Mild to moderate adverse events that are unexpected but not related to the study will be reported to IRB in the periodic review.
- Expected adverse events that are not serious will be reported to the IRB in the periodic review.
- A written periodic review will be submitted to the IRB for continuing review annually.
- All adverse events at all performance sites will be reviewed by the principal investigator.

Safety reviews. The Principal Investigator ([name], MD) will review the safety and progress of this study on a bi-monthly basis. She will report to the Institutional Review Boards, Safety Officer and Patient Advocates, any adverse event of moderate or greater severity, and a Data Safety Monitor Board if appointed by the NIH, and FDA. She will review the study and potential new literature on an ongoing basis to ensure no new information is present to cause early study termination.

In time safety– in addition all information including medical history, physical examination and laboratory assessment will be assessed by a study investigator as collected or completed by the laboratory. Summary data will be reviewed bi-monthly by the Principal Investigator ([name]).

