## **Statistical Plan**

**Sample Size and Data Analysis:** The study will use a single site randomized, double-mask design. Our primary analysis to examine the effect of betaine supplementation will be by change from baseline to 3-month values compared to placebo in completer analysis for all endpoints of Aims 1-3. Safety will be assessed by intention to treat. Prior to data analysis, the data will be examined for outliers. Continuous measures whose distributions are not symmetric will be transformed. In secondary analysis for all outcomes we will determine if baseline betaine determines response to supplementation.

*Insulin Sensitivity*-Basis for power calculations: In an overweight prediabetes population of 14 persons similar to that proposed in this grant and using a similar clamp protocol, we demonstrated insulin sensitivity of  $5.9 \pm 2.1$  mg/kg/min, a value significantly lower than  $8.3 \pm 1.8$  in our normoglycemic control group of 27 patients ( $P=0.0005$ ). This demonstrates likelihood that the cohort proposed will be insulin resistant. We also recently assessed insulin sensitivity by clamp before and after *placebo* in a cohort of 29 persons with impaired glucose tolerance in another 3-month randomized study. Baseline values were  $4.0 \pm 1.5$  mg/kg/min and 3 months later  $4.1 \pm 1.7$ ,  $P=0.3$ . The placebo change over time was  $0.16 \pm 0.81$ , or variance  $<4\%$ . This demonstrates the high reproducibility of clamp measures. A total of 30 patients entering this two-treatment parallel-design study, provides 80% probability of detecting a treatment difference at a paired two-sided comparison with type 1 error 0.05 significance, if the standard deviation is 0.81 and the true difference between treatments is 0.85 mg/kg/min (a between-group difference of 20% change from baseline). Given the short duration of the study, we anticipate  $\geq 80\%$  retention rate, but even 24 completers would detect difference between treatment groups of 0.96 mg/kg/min (25% change from baseline between groups).

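### The same safety events end study participation in one Protocol list and study therapy in another, and neither list says whether safety observation continues

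*Protocol*

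**What the plan says.** The Protocol has two lists of near-identical triggers.

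- **Research Design and Methods**, answering the form's request for objective criteria for removing a subject: "Participants will be withdrawn from the study for the following reasons". Five reasons follow: withdrawn consent, allergy, a renal or liver change, a newly diagnosed exclusion condition, and an intolerable adverse event.
- **Data and Safety Monitoring**, under a lead-in that reads "Rules for stopping the trial in the event that expected or unexpected adverse events arise": "Study therapy should be discontinued for any of the following reasons". The same five reasons appear in a different order, followed by a sixth: "Pregnancy or unwillingness to use appropriate contraception".

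Two triggers are worded identically in both places: "Acute change in renal function (eGFR decline >50%, validated) or liver function (> 3-fold increase in ALT or AST" and "Intolerable adverse event as judged by investigator and participant".

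On analysis, the SAP (Statistical Plan, Sample Size and Data Analysis) uses completers for all efficacy endpoints but says "Safety will be assessed by intention to treat". It does not define the safety set, the period over which events count, or the handling of data after a participant leaves.

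On reporting, Data and Safety Monitoring sends all adverse events to the IRB and requires dropout reasons in the annual report. Its serious-event category includes birth defects: "and event resulting in congenital anomaly/birth defect will be reported within 24 hours".

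**The concern.** Stopping the study product and leaving the study are different events for a statistician. After the first, a participant can still supply safety data; after the second, usually not. Here one set of triggers leads to each action, depending on which section the site reads, and a third action (stopping the trial) appears in the lead-in to the second list. A site facing a threefold rise in ALT has two instructions.

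If the withdrawal wording is followed literally, observation ends for exactly the participants who showed a signal. What may be lost is whether the abnormality resolved or worsened, whether anything else followed, and the safety values at the end of treatment. If such withdrawals were more frequent in one arm, the loss would be unequal. An assessment by intention to treat is informative only to the extent that everyone randomised is observed.

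Pregnancy adds a smaller inconsistency. It ends therapy in one list and is not named in the other. Birth defects are a reportable category, yet a birth outcome would ordinarily fall after a 3-month study, and nothing says whether contact is kept until then.

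**Working it through.** **1. The two lists side by side**

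| Reason | Research Design and Methods | Data and Safety Monitoring |
|---|---|---|
| Withdrawn consent | leaves the study | therapy stops |
| Allergy | leaves the study | therapy stops |
| eGFR fall >50%, or >3-fold ALT/AST | leaves the study | therapy stops |
| New exclusion condition | leaves the study | therapy stops |
| Intolerable adverse event | leaves the study | therapy stops |
| Pregnancy or contraception refused | not named | therapy stops |

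All five reasons in the first list recur in the second, which has one more. Four of the five are safety or medical events; the fifth is the participant's own decision. The stated action differs in every shared row.

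**2. What each list says about observation afterwards**

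Nothing in either case. The first implies an end to participation by its wording. The second does not say that visits or safety tests continue, and one of its own items is withdrawal of consent to take part. The main assessments are at baseline and after 12 weeks. Laboratory tests are promised at predetermined intervals that are not listed; I assume that one falls at week 12. No section describes contact after an early stop.

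**3. Size of an arm**

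The plan's own sample size reproduces. With SD 0.81, difference 0.85 mg/kg/min, two-sided 0.05 and 80% power:

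n per arm = 2 × (1.960 + 0.842)² × 0.81² / 0.85² = 2 × 7.851 × 0.6561 / 0.7225 = 14.3, rounded up to 15.

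That gives 30 in total at 1:1 allocation, as stated. Nothing in this point changes that number.

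**4. What is kept and what is lost**

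The documents give no rate for these withdrawals, so the counts below are assumptions.

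| Withdrawn for a listed event in one arm | Events counted, all randomised | Participants left with week-12 safety values |
|---|---|---|
| 1 | 1/15 = 6.7% | 14 of 15 |
| 2 | 2/15 = 13.3% | 13 of 15 |
| 3 | 3/15 = 20.0% | 12 of 15 |

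The middle column is intact because the triggering event comes before the withdrawal and is reported. The right-hand column assumes no other losses. It is where the damage lies, together with later events and resolution.

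**The case against.** The strongest reply is that these are two answers to two prompts on an IRB form, one about removing subjects and one about stopping rules, and that the author meant one rule. That is plausible. It explains the discrepancy without removing it, since the actions differ and a site must pick one.

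Several stronger inferences are tempting, and the documents do not support them.

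- *The intention-to-treat safety assessment cannot be done.* It can. All 30 participants can be analysed as assigned, and adverse events, including those that trigger withdrawal, are reported to the IRB.
- *Safety results would describe only those who tolerated treatment.* Not for adverse-event incidence, because a participant withdrawn for an event still counts as an event in that arm. A completer set would hide it (0/14, 0/13 or 0/12 for the counts assumed above), but the SAP uses completers for efficacy only.
- *No follow-up would be lost under the therapy-discontinuation list.* That list never says that follow-up continues.
- *Betaine participants would be removed in much larger numbers.* The Protocol cites gastrointestinal events in 33% on betaine and 9% on placebo, which at 15 per arm is 0.33 × 15 = 5.0 against 0.09 × 15 = 1.35 participants. How many would be intolerable is nowhere stated. The Protocol describes the liver-disease studies as using 20 g/d for 12 months, twice the daily amount and four times the duration here. In the same study, voluntary withdrawals were nine in each group. In the smaller cited study, the four of 10 patients with adverse events all completed the year. An imbalance is possible but not established.
- *The abnormal value is necessarily the last one recorded.* The eGFR criterion asks for validation, which suggests some confirmation.
- *Pregnancy is left out of the withdrawal list altogether.* Pregnancy is an exclusion criterion, so the item on new exclusion conditions may cover it. The birth-defect category is a reporting rule with no end date; early exit leaves it uncertain but does not defeat it.

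What stands is that the two actions conflict and that observation after stopping is undefined under both.

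**Conclusion.** The concern holds as an internal contradiction with a limited consequence. Four safety or medical triggers, plus withdrawn consent, carry two different actions; pregnancy or contraception is named in only one list; and neither list says whether observation continues. If participation ends at the trigger, the intention-to-treat safety assessment keeps the triggering events but may lack later events, resolution and week-12 safety values for those participants.

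The size cannot be estimated from the documents. Each such withdrawal is 1/15 = 6.7% of an arm, and whether the arms would differ is unknown. The conclusion rests on reading the withdrawal list literally and on safety laboratory tests being due at week 12. It concerns safety data only; the sample size and the choice of efficacy analysis set are not affected.

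**What to change.** Reconcile the two Protocol lists into one that states separately what ends study therapy and what ends study participation, and separate both from rules for stopping the trial. State that safety data collection through week 12 continues for participants who are off study therapy but have not withdrawn consent, so that the SAP's intention-to-treat safety assessment has data to work on. Reconcile the handling of pregnancy across the two lists and with the congenital-anomaly reporting category.

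Which events end treatment or participation, and how an abnormality is managed, is for the investigators to decide; the request is only that the passages agree.

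The cost is a wording change and a few extra safety contacts. Some participants off therapy will decline those contacts, so some data will still be missing.
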